1.2.2 Equivalency Tests

We will follow standard procedures in cleaning data and examining initial distributional properties (means, standard deviations, medians, skew, kurtosis) in addition to graphical summaries (boxplots and density plots). Subsequently, we will evaluate the success of randomization by testing between-condition differences with respect to demographic covariates and primary outcomes reported at baseline. Note, because participants are nested within dyads, these analyses will utilize the Generalized Estimating Equation (GEE) module within SPSS to

control for the non-independence of observations and specify outcome distributions that are appropriately matched to the variables of interest.

Finally, we will conduct an analysis of attrition to determine if dropout at each follow-up time-point is associated with (1) demographic variables assessed at baseline and/or (2) drug use or TRB outcomes assessed at baseline. At each wave, we will utilize GEE models to evaluate whether those participants retained at the given wave differ significantly with respect to demographic or baseline outcome values compared to those who were not retained. As with the analyses of randomization success, the use of GEE permits analyses to control for the nesting of participants within couples and specify outcome distributions that are matched to variables of interest. Factors which are observed covary significantly with attrition will be incorporated as covariates in outcome analyses. Mplus has a variety of options for handling partial attrition including full-information maximum likelihood estimation [56]. Non-random and consequential missingness can also be modeled directly through the addition of latent variables which account for the probability of missingness at any time point. Where indicated, we will explore the use of these procedures in the analyses described below.

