Baseline Visit – PHASE 2 (up to \$50)

1. Informed Consent process
2. STI testing (\$20)
3. CASI survey (\$10)
4. Randomization to one of three conditions (phase 2)
5. Session 1 (phase 2): will occur at this time in accordance with the randomized condition.
 - a. Condition 1: CHTC
 - b. Condition 2: ACT videos + CHTC
 - c. Condition 3: MI-CST + ACT videos + CHTC

FOR COUPLES WHO ARE ASSIGNED TO A CONDITION THAT INCLUDES VIDEOS, PARTICIPATING COUPLES WILL WATCH THE VIDEOS SEPARATELY. AFTER VIEWING THE VIDEOS SEPARATELY, A VIDEO RECOGNITION SURVEY (ATTACHED) IS COMPLETED BY THE COUPLE TOGETHER.

Baseline Visit – PHASE 3 (up to \$50)

1. Informed Consent process
2. CASI survey (\$30)

PROTOCOL TITLE:

3. Randomization
4. HIV testing (\$10)
5. STI testing (\$10)
6. Session 1: will occur at this time in accordance with the randomized condition.
 - a. Condition 1: individual HIV testing (IHTC) as usual condition
 - b. Condition 2: We Test intervention

Randomization Stratification: Randomization will be stratified by Site, Age (either partner under 18 vs both 18 & older), Race/Ethnicity (Both White vs not both White) and whether the index partner attended individual vs couple.

After completing the baseline assessment for both Phases 2 and 3, YMSM will complete follow-up assessments a month after baseline, and 3 months after baseline. In Phase 3, participants will also complete assessments at 6-months post-baseline. Online CASIs will be completed at each follow-up either at home or in-office. In addition, STI and HIV testing will occur at the 3-month and 6-month follow-ups. All follow-ups will be conducted individually to facilitate retention, even if the couples dissolve.

Immediate Post-Test Assessment (1 month after BL)

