1.2 Quantitative Analysis Plan

The primary hypothesis is that due to developing skills in self-management and assertive communication, inclusion of adjunct components will be associated with clinically significant decreases in HIV transmission risk behavior (TRB) as compared to partnered YMSM who receive CHTC (only). Secondarily, we propose that these intervention effects will be mediated by assertive communication skills. As stated above, we focus on four behavioral indicators of TRB. At the individual-level, we examine: (1) number of CAS acts with a casual partner in the absence of PrEP and (2) any positive chlamydia or gonorrhea diagnoses in the absence of PrEP. At the couple-level, we will examine (3) any sex in the absence of PrEP with a primary partner who reports CAS with a casual partner; and (4) any sex in the absence of PrEP with a primary partner who receives a positive chlamydia or gonorrhea diagnosis. Any missing data and additional covariates will be informed by attrition analyses prior to primary analyses.

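### Baseline risk enters the outcome models only if it significantly predicts dropout pooled across arms, a test that can miss dropout depending on arm together with baseline risk

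*SAP*

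**What the plan says.** SAP 1.2.2 (Equivalency Tests) plans GEE models of dropout at each follow-up. The first predictor set is demographic: "we will conduct an analysis of attrition to determine if dropout at each follow-up time-point is associated with (1) demographic variables assessed at baseline". The second is "2) drug use or TRB outcomes assessed at baseline". Condition appears in neither. The only comparison of arms in that section is the check of baseline balance. The outcome of the dropout models is one status per wave, "whether those participants retained at the given wave differ significantly with respect to demographic or baseline outcome values compared to those who were not retained", and neither document defines retained.

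These models matter because of what follows from them. SAP 1.2 states "Any missing data and additional covariates will be informed by attrition analyses prior to primary analyses". SAP 1.2.2 gives the rule: "Factors which are observed covary significantly with attrition will be incorporated as covariates in outcome analyses". Full-information maximum likelihood (FIML) and latent missingness models are named as available, but the commitment is "Where indicated, we will explore the use of these procedures in the analyses described below".

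SAP 1.2.1 describes the primary model as a latent growth curve fitted to follow-up data, with growth factors regressed on condition. It names no baseline-value covariate.

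Protocol 6.0 has STI testing at months 3 and 6 as an item separate from the survey and separately paid. On the survey it says "Online CASIs will be completed at each follow-up either at home or in-office". Protocol 8.0 has remote STI samples sent back to a central laboratory.

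**The concern.** Baseline TRB is likely to be a strong predictor of follow-up TRB, yet whether the models adjust for it depends on a significance test of a different question: does it predict dropout when the arms are pooled? The Phase 3 arms differ greatly (motivational interviewing, video and couples testing against usual individual testing), so the kind of person who leaves may differ by arm. If high-risk participants tend to leave one arm and low-risk participants the other, the two patterns offset each other in the pooled test. Baseline TRB then stays out, and the arms compared at follow-up have a different risk mix.

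A second loss may also go unseen. Two of the four TRB indicators in SAP 1.2 rest on a chlamydia or gonorrhoea result, one participant's own and one the partner's. Someone who completes the survey at home but returns no specimen has no result for these, and a single retention status need not show it.

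**Working it through.** **Retention in the plan.** SAP 1.2.2 (Power Analysis) expects at least 232 of 288 individuals at 6 months: 232/288 = 80.6%, so 19.4% lost. It is given overall, not by arm or data source. The risks and arm-specific losses below are assumptions.

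**Arm-only dropout.** With losses of 9.4% and 29.4% by arm, unrelated to risk or outcome, the odds ratio (OR) under no effect stays at 1.00.

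**Extreme illustration, no true effect.** One third of participants are high-risk (event risk 0.40) and two thirds low-risk (0.10), so true risk is 0.20 in both arms. We Test loses 40% of high-risk and 10% of low-risk participants; individual testing (IHTC) loses 0% and 30%.

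- Retained: We Test 1/3 x 0.6 + 2/3 x 0.9 = 0.80; IHTC 1/3 x 1.0 + 2/3 x 0.7 = 0.80.
- Pooled dropout: high-risk (40% + 0%)/2 = 20%; low-risk (10% + 30%)/2 = 20%. The planned test has nothing to detect, and neither has a test of arm alone.
- Observed risk, We Test: (1/3 x 0.6 x 0.4 + 2/3 x 0.9 x 0.1)/0.80 = 0.14/0.80 = 17.5%.
- Observed risk, IHTC: (1/3 x 1.0 x 0.4 + 2/3 x 0.7 x 0.1)/0.80 = 0.18/0.80 = 22.5%.
- Observed OR: (0.175/0.825)/(0.225/0.775) = 0.73.
- Within each risk group the risk is the same in both arms, so adjusting for baseline risk returns an OR of 1.

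**Less exact cancellation.** Same risks and We Test losses, only the IHTC losses changed; one visit, individuals treated as independent.

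| IHTC loss, high / low risk | Pooled dropout, high / low risk | Unadjusted OR | Chance that the planned test flags baseline risk, N=200 / N=288 |
|---|---|---|---|
| 0% / 30% | 20% / 20% | 0.73 | 5% / 5% |
| 10% / 25% | 25% / 17.5% | 0.79 | 25% / 33% |
| 20% / 20% | 30% / 15% | 0.85 | 69% / 83% |
| 30% / 15% | 35% / 12.5% | 0.92 | 95% / 99% |

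**Milder shifts.** Half are at high baseline risk, event rates are 50% and 15%, there is no true effect, and 19.4% are lost in each arm. Loss by risk group moves 10 points either side of 19.4%, in opposite directions by arm. Observed risks are 30.3% and 34.7%, OR 0.82. In 6,000 simulated trials per size (one visit, independent individuals), the results at N=200 and N=288 were:

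- pooled test flags baseline risk: 4% and 5%;
- test of arm alone flags dropout: 5% and 6%;
- arm x baseline-risk test flags dropout: 95% and 99%;
- type I error of the unadjusted comparison: 10% and 11%, against a nominal 5%.

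If the 10-point shift occurs in one arm only, the OR is 0.90, and the pooled test (43% and 58%) does almost as well as the interaction test (45% and 60%).

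**STI results.** At the SAP's retention rate, the protocol's 200 individuals give 200 x 232/288 = 161. If 20% of those lacked a specimen (assumed), 161 x 0.8 = 129 would have an STI result while retention still read 81%.

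**The case against.** The strongest objection is that 0.73 is not what the planned analysis would produce. It is a crude proportion at one visit, whereas the SAP plans a multilevel growth model and names FIML, which uses the earlier waves of people lost later. If baseline were a time point in the growth curve, the bias would shrink for condomless sex, though the SAP describes follow-up data only. This stands: the figures show a mechanism and do not forecast the trial's bias.

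Next, the extreme case needs nearly exact opposition between arms, which no document suggests. As opposition weakens, the planned test increasingly finds baseline risk and brings it in by the SAP's own rule. This also stands; the gap is widest where the patterns largely cancel.

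Three stronger readings are tempting, and the documents do not support them:

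- That unequal dropout by arm is itself the bias. Condition is already in the outcome model, and arm-only dropout left the OR at 1.00.
- That the attrition tests are the sole gate to missing-not-at-random models. The SAP states no trigger for these.
- That a participant with a survey and no specimen counts as retained. The term is undefined, so this is possible but not stated. An absent specimen would presumably be a missing outcome in the STI model, and home kits and a central laboratory (Protocol 6.0) reduce access losses.

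**Conclusion.** The concern holds in a limited form. Adjustment for baseline TRB is left to a significance test that pools the arms, and no baseline-value covariate is otherwise committed. Where dropout depends on arm together with baseline risk, following the plan can leave a bias that baseline adjustment would remove or reduce. Under the assumptions shown, a null effect appears as a crude OR of about 0.82 with 10-point opposite shifts and 0.73 in the extreme case. Likelihood estimation may lessen this. The actual size cannot be known, because the documents give no dropout by arm, STI completion or base rates. The STI part is narrower: retention is undefined and one status may conceal missing STI outcomes, to an unknown extent.

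**What to change.** Amend SAP 1.2.1 and 1.2.2 before analysis:

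1. Include baseline TRB as a pre-specified covariate in the primary models regardless of attrition p values, and the baseline STI result for the STI outcomes. This is the main change. Protocol 6.0 lists Phase 3 baseline STI testing after randomisation, so report its completion by arm.
2. Add condition and condition x baseline TRB to each attrition GEE. A condition term alone would miss the patterns above. The interaction test can also miss one-sided patterns, so it supplements item 1 and does not replace it.
3. Define completion separately for the survey and the STI specimen, and report and model each by arm and wave.

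A missing-data sensitivity analysis is desirable, but its form should be simple and feasible at this trial's size. STI outcomes have only two follow-up points, so a mandatory latent missing-not-at-random model is not proposed.

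The cost is SAP wording and a few extra models on data already collected, with no added work for sites or participants.
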